The StepRite system developed by MedHab (<http://www.medhab.com/>) allows the physical therapist to monitor physical activity and exercise remotely, thereby reducing the need for frequent out-patient visits. A thin insole placed inside the shoe measures foot contact pressure and acceleration. This information is translated into quantitative feedback about exercise compliance and performance measures comparing the surgical side with the non-surgical side. Real time feedback during exercise and weight-bearing activities is

provided to the patient, and a HIPAA secured user interface website also displays this information in an online dashboard for both physical therapists and the physician.

With the advent of federally mandated bundled payments for total joint replacement, active management of the rehabilitative process postoperatively with quantifiable data will be necessary to ensure financial stability.

Given the potential for improving patient engagement with rehabilitation, this study proposes a treatment model which includes monitoring activity outside of the clinic using the StepRite device and using a combination of outpatient appointments and remote consultations with therapists.

Significance of this study

The significance of the proposed study includes the projected benefit to the patients in terms of attaining clinical outcomes quicker and to the medical system in terms of managing cost for the provision of services. Subjects are expected to demonstrate improved compliance to patient tailored rehabilitation protocols which will lead to more rapid attainment of clinical outcomes versus present traditional rehabilitation methodologies. The expected level of, and rate of, attainment of clinical outcomes will translate to an overall reduction of cost to the medical system by reducing the need to engage in additional processes or the need to protract the time required to attain clinical outcomes, where either or both in combination can increase rehabilitation expenditures.

Objectives

To compare the efficacy of StepRite in a prescribed physical therapy program verses traditional in-facility physical therapy program after partial or primary total knee replacement using validated survey tools to evaluate patient progress, including patient self-reporting of progress and surgeon appraisal of patient performance post-operatively.

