To compare the overall cost of post-operative rehabilitation of patients involved in traditionally employed regimens versus those using the StepRite device.

Hypothesis and specific aims

The aim of this study is to evaluate whether improved clinical outcomes as well as reduction in cost in provision of care can be better affected through the use of the Steprite device as compared to the use of traditional rehabilitation modalities.

We will seek to reject the null hypotheses that 1) there is no difference between clinical outcomes attained between patients using the Steprite device and those using traditional rehabilitation modalities and that 2) there is no reduction in cost to the medical system when patients use Steprite versus other conventional methods of rehabilitation.

By rejecting the null hypothesis we will accept the alternate hypothesis that, through the use of the Steprite device, not only will patients achieve overall clinical outcomes faster but there will be an associated decrease in cost burden to the medical system and the differences observed will be statistically significant as compared to rehabilitation of patients not using the Steprite device.

Patients who use the device post-surgery will demonstrate superior short-term improvements (i.e. 3 months post-surgery) with respect to self-reported functional outcomes and gait parameters, compared to a control group not using the device. The patients will self-report through the use of validated survey instruments including the KOOS survey (knee injury and osteoarthritis outcome score), LEFS (lower extremity functional scale) and/or KSS (knee society score), the latter of which includes a section for surgeon evaluation of patient functionality post operatively.

Study Design and Methods

This is a point of care clinical trial; a trial that functions to integrate research within a clinical setting that has the ability to readily deliver either modality of the proposal. This type of study design relies on provider referral of patients to be approached for consent, after which randomization to one of two treatment groups is facilitated; a control group of 15 patients participating in conventional rehabilitation regimens and an experimental group of 15 patients who will participate in the same rehabilitation regimen but facilitated

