Both groups will be given log sheets to record their activity at home and when seen by the physical therapist. These will be returned and collected by the therapist weekly and scanned into/ kept in the patient's medical record file. A paper copy will be kept in the coordinator's office, 4A144B with the consent forms and any other study documents.

Both groups will also have routine self-assessment questionnaires (appendices 3, 4 KOOS and KSS) and functional testing performed by the PI and PT during the patient's regular clinic visit as standard of care.

Outcome measurements performed just after surgery and at time of discharge from hospital and standard of care post-surgical clinic visits to 8 weeks will indicate if any patients are experiencing unexpected delays in progress. Subjects will be visited at home by the Home Health therapists, and will visit and receive telephone consultations with the outpatient therapists, who will be able to monitor the patients' conditions and intervene if there are any problems related to the use of the device. The StepRite device will provide the therapist with more information about the patients' activity levels and progress than would usually be available to them and so is not expected to have any safety implications. The device and App. will prompt the patient with voice and text to complete their exercises as they are needed, while collecting data.

Device Flow Chart: standard of care post-op

The research coordinator will consent the patient prior to the surgery

The research coordinator will document the following information for the device on the device data collection form. (See attached)

- a. Name of patient
- b. Email of patient
- c. Phone number of patient
- d. Surgery date
- e. Expected date of discharge

The patient's information will then be entered into the steprite™ system and a patient account will be created by the Research Coordinator

Physical therapy will schedule the study protocol via the steprite™ system and enter the physical therapy start date as day after discharge.

MedHab™ sponsor ([name]) will contact the patient for the patient account set up and to obtain the following signatures required by MedHab (see attached)

- a. HIPAA
- b. Assignment of Benefits

MedHab™ will help the patient load the app, provide an overview of the app, and forward a tutorial video
MedHab™ will send the steprite™ device to the study Research Coordinator at TTUHSC

TTUHSC Orthopaedic Surgery

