Clinical Trials Coordinator, [name]

[name]

(t)[contact] (f)[contact]

The Research coordinator will fit the patient with the device, pair, and connect the device at time of discharge.

Patient will leave the hospital with the steprite™ device and instructions to charge device overnight for use the next day.

Patient will begin exercise regimen prompted by the StepRite App on the cell phone.

Physical therapy will communicate with the patient per the therapy protocol

Physical therapy is to work with patient per standard of care protocol with the addition of 3 patient outcome surveys, (KOOS, KSS, and the Lower Extremity functional scale) (see attached) at 4, 6, and 8 weeks post op, and the PI will see the patient as standard of care at visits 2, 6, and 12 weeks post-op. The 2 week patient outcome surveys will be completed at the 2 week standard clinic visit with the assistance of the study coordinator. All documents and data collection forms from physical therapy and clinic will be

scanned into the patients chart for review and kept in a locked file cabinet in the research coordinators office 4A144B.

Physical therapy advises the PI and MedHab two weeks prior to close of therapy on close out or extension procedure if needed.

The PI and MedHab extends the therapy or communicates the close out procedure with the patient.

Control Subject flow

The control group will have all Post-op standard of care as the device group without the use of the device.

Device Information

The device to be used in the study is the StepRite, manufactured and supplied by Medhab LLC. The device is considered exempt from IDE regulations, as it is a diagnostic device. It has been approved as a Class I medical device by the FDA.

The StepRite device consists of a thin insole which is placed inside the shoe.

The insole contains pressure sensors which record pressure data when exercises are performed, and contains an accelerometer, which records acceleration of the foot and is used to calculate velocity and activity levels.

A wireless connection between the insole and a cell phone application allows transfer of data.

The cell phone application will be supplied.

The cell phone application displays real-time feedback of pressure distributions to the user, and connects wirelessly to the Medhab servers to upload data onto the secure web interface, for access by the physical therapist or physician.

The device does not impart energy to the user.

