There is a risk of loss of confidentiality, we will have measures in place to help prevent any loss of personal information. During the course of this study there are no new or additional steps required of the subjects from what is considered the standard protocol for the lead investigator. The only alteration may be reduced travel and outpatient visit by the patient if compliance and functional improvement noted by the therapist. StepRite imparts no energy to the patient and poses no hazard to patient well being. Subjects will be free to withdraw from the study at any time and revert to conventional rehabilitation treatment.

Possible benefits to subjects

There is a possibility the device group patient could benefit from the device prompting them to do their own exercises regularly, which could lead to a faster recovery and better physical therapy outcomes. We are hoping the participation in this study may help us learn how we can design rehabilitation programs to be more effective in the future.

Confidentiality measures

StepRite / MedHab will have access to non-PHI patient data collected by the device stored on their HIPPA compliant server and be available only to the lead investigator. All PHI will be kept separate from the study data in a locked filing cabinet or on a password protected computer in the research coordinators office in 4A144B.

Data Collection and Monitoring

Data recorded by the StepRite device will be transmitted wirelessly to the HIPAA secured web interface managed by Medhab. Clinicians will be able to log into the website with a password to review the progress of each patient.

Data recorded by the PI and physical therapist on the functional motion of the knee will be recorded in paper form and kept with the completed KOOS questionnaire and Knee Society Score (KSS) and scanned into the patients HIPPA protected chart.

Upon completion of patient's part in the study MedHab will contact UMC and the Therapy departments to acquire actual costs of these services. This will be done to compare the overall cost of management of the post-operative rehabilitation of a patient in traditional rehabilitative regimen vs. use of StepRite,

Actual Cost information for the patient's full rehabilitation will be requested and collected by the Hospital and released to MedHab at the end of the study and supplied to the lead investigator for analysis.

References

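### The KSS carries the surgeon appraisal, but weeks 4 and 8 have no surgeon visit or named rater and week 12 has no dated KSS, so dated surgeon appraisal stops at week 6 although the hypothesis is at 3 months

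*Combined protocol and SAP*

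**What the plan says.** The Objectives define efficacy through validated survey tools, "including patient self-reporting of progress and surgeon appraisal of patient performance post-operatively". Under Hypothesis and specific aims the KSS is listed with the KOOS and LEFS and described as an instrument "the latter of which includes a section for surgeon evaluation of patient functionality post operatively". Neither of the other two is described as having a surgeon section. The same section places the expected benefit at 3 months after surgery.

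The Device Flow Chart says that physical therapy follows the standard-of-care protocol "with the addition of 3 patient outcome surveys, (KOOS, KSS, and the Lower Extremity functional scale) (see attached) at 4, 6, and 8 weeks" after surgery. The same sentence continues: "the PI will see the patient as standard of care at visits 2, 6, and 12 weeks post-op". It then adds: "The 2 week patient outcome surveys will be completed at the 2 week standard clinic visit with the assistance of the study coordinator". The instruments in the week 2 set are not listed again.

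The Schedule of events groups the KSS with the KOOS as "routine self-assessment questionnaires (appendices 3, 4 KOOS and KSS" and pairs them with "functional testing performed by the PI and PT during the patient's regular clinic visit as standard of care". Its next paragraph has outcome measurements at clinic visits running only to 8 weeks.

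**The concern.** An instrument with a surgeon-rated part has been put on a survey schedule that does not match the surgeon's visits. A site following the Device Flow Chart at weeks 4 and 8 cannot tell whether the surgeon section should be left blank, filled in by a therapist, or not attempted. At week 12, when the surgeon does see the patient, no KSS is called for.

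At stake is the surgeon-appraisal part of the objective. Followed literally, the dated schedule produces none after week 6 and none at the time point of the hypothesis. If therapists fill in the section at some visits and surgeons at others, change from visit to visit would partly reflect the change of rater.

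**Working it through.** The plan states no figure to reproduce. The check compares two sets of weeks.

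Inputs, all from the Device Flow Chart unless noted:
- KSS in physical therapy: weeks 4, 6 and 8.
- Further survey set: week 2, assumed to include the KSS.
- PI visits, taken as the surgeon's visits: weeks 2, 6 and 12.
- Time point of the hypothesis (Hypothesis and specific aims): 3 months. Week 12 is the nearest scheduled visit.

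| Week | KSS dated? | Setting | PI visit? |
|---|---|---|---|
| 2 | assumed | clinic, coordinator assisting | yes |
| 4 | yes | physical therapy | no |
| 6 | yes | physical therapy | yes |
| 8 | yes | physical therapy | no |
| 12 | no | none stated | yes |

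1. Dated KSS weeks without a PI visit: {2, 4, 6, 8} minus {2, 6, 12} = {4, 8}. That is 2/4 = 50%.
2. If week 2 is not counted: {4, 6, 8} minus {2, 6, 12} = {4, 8}. That is 2/3 = 67%.
3. PI visits without a dated KSS: {2, 6, 12} minus {2, 4, 6, 8} = {12}.
4. Weeks with both: {2, 6}. The latest is week 6, and 6/12 = half-way to the week 12 visit.
5. Cross-check with the Schedule of events: PI visits falling within its 8-week limit on outcome measurements are weeks 2 and 6, so that section does not supply week 12 either.

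Step 4 is favourable to the plan. At week 6 a PI visit falls in the same week as the physical-therapy survey, but no sentence says that the surgeon completes the surgeon section then. The outcome measurements just after surgery and at hospital discharge are not counted, because their instruments are not named. They come before week 2 and would not change step 4.

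**The case against.** The best reply is that the intended arrangement may already be sensible. The Device Flow Chart calls the physical-therapy forms patient surveys and mentions the PI's visits separately, and the Schedule of events separates questionnaires from functional testing. On that reading patients complete their part in therapy and the surgeon appraises in clinic. This is plausible, and it reduces the week 4 and 8 problem to one of wording. It does not supply a KSS at week 12. The Schedule of events attaches the KSS to regular clinic visits without dates, so week 12 could be meant, but its next paragraph stops outcome measurements at 8 weeks.

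Four stronger inferences are tempting and are not supported:
- **That the surgeon section can be scored only at PI visits.** No sentence says so. The KSS form is an attachment that is not shown, so its version, layout and rater instructions cannot be checked. Therapists also take part in functional testing, and Data Collection and Monitoring states: "Data recorded by the PI and physical therapist on the functional motion of the knee will be recorded in paper form". A therapist might score the section, although that would not be the surgeon appraisal named in the objective.
- **That the 50% converts into a count of forms across the whole trial.** This would need the week 2 set to include the KSS, no attrition, and controls on the same dates. The dates appear only in the Device Flow Chart, while the Control Subject flow promises controls the same standard post-operative care without dating any survey.
- **That a change of rater biases the comparison between arms.** The planned analysis is a two-group t-test, and the same therapists serve both arms. A rater change at a given week that is common to both arms does not by itself bias a same-week comparison. Only change across visits would be affected, and no such analysis is specified.
- **That the KSS is optional, so nothing is lost.** The hypothesis does join it to the LEFS by and/or, which leaves its weight unclear. But the Schedule of events, the Device Flow Chart and the data-collection section all include it, and it is the only instrument described as carrying the surgeon's rating.

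**Conclusion.** The point holds as a mismatch of schedule and rater. Two of the 4 dated KSS points (2 of 3 without week 2) have no scheduled surgeon and no named rater. The latest dated KSS that coincides with a surgeon visit is week 6, and none is dated at the 3-month point of the hypothesis. As scheduled, the plan does not produce a dated surgeon appraisal at the time it wants to test.

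This assumes that the week 2 set includes the KSS, that the PI's visits are the surgeon's visits, and that week 12 stands for 3 months. The week 12 gap does not depend on the first of these. The documents do not show that every KSS at weeks 4 and 8 would be invalid, or that the comparison between arms would be biased.

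**What to change.** In the Device Flow Chart, and explicitly for both arms, state who completes each KSS section at each week:
- The surgeon scores the surgeon section at the existing week 2, 6 and 12 visits.
- The patient section is also collected at week 12, so that a full KSS exists at 3 months.
- Only the patient section is collected at weeks 4 and 8.
- The two sections are reported as separate scores. The surgeon-appraisal comparison is based on week 12, with week 6 as supporting.
- The Schedule of events no longer describes the KSS as purely self-assessment, and its 8-week limit on outcome measurements is reconciled with the week 12 collection.

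Basing the comparison on week 12 is a recommendation that follows from the 3-month hypothesis; the protocol itself sets no week for surgeon appraisal.

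The cost is protocol wording, a change to the data form, and one extra form at a visit that already takes place. The downside is that no full KSS is available at weeks 4 and 8.

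### Staff who set up StepRite or can see its data also assist with the surveys and rate function, and no safeguard is stated, so part of a difference in KOOS, LEFS, KSS or functional tests could be helper or examiner expectation

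*Combined protocol and SAP*

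**What the plan says.** **Coordinator.** In the section Device Flow Chart: standard of care post-op, the research coordinator creates the patient's StepRite account. At the end of the hospital stay, "The Research coordinator will fit the patient with the device, pair, and connect the device at time of discharge". The same section then says of the first follow-up: "The 2 week patient outcome surveys will be completed at the 2 week standard clinic visit with the assistance of the study coordinator".

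**Physical therapy.** The flow chart says "Physical therapy will schedule the study protocol via the" StepRite system. For weeks 4, 6 and 8 it says "Physical therapy is to work with patient per standard of care protocol with the addition of 3 patient outcome surveys", namely KOOS, KSS and LEFS. Study Design and Methods has the same therapists treating both arms.

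**Examiner-rated measures.** Schedule of events gives both groups "functional testing performed by the PI and PT during the patient's regular clinic visit as standard of care". Hypothesis and specific aims lists KOOS, LEFS and/or KSS as self-report, and says of the KSS: "the latter of which includes a section for surgeon evaluation of patient functionality post operatively".

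**Access to device data.** Background describes a website that "displays this information in an online dashboard for both physical therapists and the physician". Device Information and Data Collection and Monitoring also give clinicians access. Confidentiality measures, however, restricts the device data to the lead investigator.

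The protocol mentions no blinded or independent assessor, no rule that patients complete surveys unaided, and no order between rating a patient and viewing that patient's device data.

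**The concern.** Patients cannot be masked to wearing an insole and using an app. What staff add to the measurements is a separate source of bias, and part of it can be avoided.

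KOOS, LEFS and the patient part of the KSS are meant to be the patient's own report. Help from the person who fitted the device, or from the therapist running its programme, can colour the answers. Functional tests and the surgeon's part of the KSS depend on an examiner's judgement. That examiner may know the arm and may have seen activity data that have no counterpart for control patients.

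The planned analysis is a two-group t-test. It cannot tell a shift produced by the device from one produced by the people collecting the data. Unlike many analysis problems, this one cannot be repaired after the data are in.

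**Working it through.** **1. Roles set side by side.**

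- Coordinator: sets up the account and fits the device; assists with the week-2 surveys. The protocol uses both research coordinator and study coordinator, and describes no second coordinator role, so I take them as one.
- Physical therapy: schedules the StepRite programme; handles the surveys at weeks 4, 6 and 8; shares the functional testing.
- Investigator: does functional testing; has access to device data.
- Surgeon: rates a section of the KSS. The protocol does not say which surgeon. It does not give this section to the therapist.

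**2. Who can see device data.** Background, Device Information, and Data Collection and Monitoring give access to therapists and physicians. Confidentiality measures gives it to the lead investigator only. These passages must be reconciled. The investigator has access on either reading; the therapist has it only on the first.

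**3. Is the help equal between arms?** The week-2 assistance is written in the device flow chart. Control Subject flow says only that controls receive the same postoperative standard of care without the device. Equal help for controls is therefore not explicit, and unequal help would make the concern stronger.

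**4. What a staff-driven shift would do.** The plan gives no figure on this point to reproduce. Its total of 30 is called a starting point and has no effect size or SD behind it, so it cannot be re-derived.

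Inputs from the plan are 15 per arm, significance level 0.05 and a two-group t-test. My assumptions are a two-sided test, no true device effect, and a shift of b SD in favour of StepRite. The documents give no value for b.

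- Degrees of freedom: 15 + 15 − 2 = 28; critical t = 2.048.
- Smallest significant difference: 2.048 × √(2/15) = 2.048 × 0.365 = 0.748 SD.
- Noncentrality: b / √(2/15) = 2.739 × b.

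| Assumed shift b (SD) | Noncentrality | Significant in favour of StepRite | Significant in either direction |
|---|---|---|---|
| 0 | 0 | 2.5% | 5.0% |
| 0.2 | 0.548 | 7.6% | 8.3% |
| 0.3 | 0.822 | 12.2% | 12.5% |
| 0.4 | 1.095 | 18.4% | 18.5% |

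A larger sample does not cure this. If all 35 requested patients were analysed (17.5 per arm on average), the two-sided rates at 0.2 and 0.3 SD would be 8.9% and 13.8%. That matters here because the plan leaves room to add patients in steps.

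**The case against.** The strongest reply is that this is a point-of-care trial. Study Design and Methods deliberately uses outcome measures already built into routine care, with the same therapists in both arms, so assessment by treating staff follows from the design. That stands as a reason not to require an outside assessor. It is no reason to leave out simple safeguards that the same staff can apply.

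Other points against the concern:

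- **Assistance is undefined.** It may mean only handing out and collecting forms, and the forms are attachments not seen here. This is fair. The text does not show that the coordinator scores anything, and the remedy is to say what is allowed.
- **Week 2 is not the hypothesised time point**, which is 3 months. True, but the therapists' role in the surveys at weeks 4, 6 and 8 and the examiner ratings raise the same question.
- **The shift is assumed, and patients' own expectation could produce it.** This stands. The table shows how sensitive the test is to a shift; it does not show what the fix would save.
- **Examiners see device data over weeks, and may know the arm anyway.** This also stands, and limits what a rule for a single visit can do.

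A reader might infer that every outcome is compromised. The documents do not support that. Cost is a separate objective drawn from hospital and therapy records. Gait parameters are named as an outcome, but the text does not say who measures them or how. A reader might also infer that the therapist scores the clinician's part of the KSS, but the protocol assigns it to the surgeon.

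**Conclusion.** The concern holds for KOOS, LEFS, KSS and functional testing. Staff who deliver StepRite, or can see its data, also assist with or rate these measures, and no safeguard is stated. Part of any observed difference could therefore be helper or examiner expectation.

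The size and direction of such bias cannot be found from the documents. Under an assumed shift of 0.2 to 0.4 SD towards StepRite, with 15 per arm, no true effect and a two-sided 0.05 test, the chance of a significant result favouring StepRite is about 8% to 18% instead of 2.5%. It would be wrong to read this as showing that a positive result would be false, or that the fix would bring the rate back to 2.5%: patients know their arm, and that source of bias stays. The conclusion also rests on reading the two coordinator titles as one role. For the therapists' sight of device data, it depends on how the conflicting access statements are resolved.

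This is a worthwhile, inexpensive improvement to the measurements. It does not make the design unworkable.

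**What to change.** 1. **Device Flow Chart.** Replace the wording on coordinator help at week 2 with a rule for both arms: patients complete KOOS, LEFS and the patient part of the KSS unaided, before seeing staff at that visit, and return them sealed. Apply the same rule at weeks 4, 6 and 8.
2. **Schedule of events.** Require that functional tests and the surgeon's section of the KSS are recorded, in both arms, with the insoles out of the shoes and before device data are opened at that visit. This helps only in part, because examiners may know the arm and have seen earlier data.
3. **Report.** State that outcome assessment was not blinded.
4. **Access.** Reconcile Confidentiality measures with the three sections that give therapists or clinicians access to device data.

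I do not propose a separate surgeon who is unaware of the arm. The protocol identifies no such person, and that would be an added resource.

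The changes need protocol wording and existing staff. The downside is a few more unanswered survey items, and the dashboard being opened slightly later in the visit.
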